The primary endpoint is the % reduction in 2-hour incremental AUC for glucose. Using the t-distribution with 2-tailed $p<0.05$ and assuming an average CV of within-individual variation of 2-hour incremental AUC values of 25%, $n=20$ subjects (10 lean and 10 overweight) has 80% power to detect a 17% difference in AUC, 90% power to detect a difference of 19% and 99% power to detect a difference of 26%. Within each subject group ($n=10$) there is 80% power to detect a difference in AUC of 25%, and 80% power to detect a 33% difference between the responses of lean and overweight subjects. To allow for 10% dropout, we will recruit $n=11$ lean and $n=11$ overweight subjects.

Subject Recruitment

Participants will be recruited from the pool of participants at GI Laboratories who have indicated that they are willing to be contacted and asked if they wish to participate in new studies. If an insufficient number of subjects can be recruited, then a newspaper advertisement will be used to recruit new subjects.

Selection of participants

Participants willing to be considered will be invited to come to the research centre to have the study procedures explained to them and be given a copy of the consent form which they may either sign then, take away to sign at a later date, or decline to participate. Participants will be encouraged to ask any questions they may have and not to sign the consent form until all of their questions have been answered to their satisfaction. Those who consent to participate will come to the research centre for a pre-selection visit when subject eligibility will be determined. During this visit, the 10-14hr overnight fasted participants will complete a questionnaire (Appendix 1) to assess medical history, and lifestyle factors, have height, weight, waist circumference and blood pressure measured, and have a blood sample drawn for measurement of glucose, HbA1c, lipids, creatinine, AST, ALT and complete blood count. Females will have a pregnancy test.

PROCEDURES

The study will have a randomized block design with repeated measures. One block, which will be double-blinded, will test the effect of Axulin capsules; the other block, which will be open label, will test the effect of Axulin tablets. Within each participant, the order of the blocks will be randomized and within each block the order of the treatments will be randomized.

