Eligible participants will be instructed to maintain stable dietary and exercise habits and for the duration of the study, to avoid vigorous physical activity for 24hr before each visit and to and consume their normal dinner the night before each visit. At each visit current use of medications and natural health products participants will be reviewed with each participant and any changes will be discussed with the investigator. Female participants will be advised that if they become pregnant during the study they are to contact the investigators and discontinue their participation immediately.

Each subject will be studied on 6 separate days with at least a 3-day interval between tests. On each test day, subjects will come to GI Labs ([name]) in the morning after a 10-14h overnight fast. On each test occasion the subject will be weighed, and give fasting finger-prick and venous blood samples. Blood from a forearm vein will be collected into a 6ml EDTA tube (Vacutainer, BD Canada, Mississauga, ON). Finger-prick blood samples will be collected into 2 separate vials: one (2-3 drops blood into a fluoro-oxalate tube) for glucose analysis and the other (6-8 drops of blood into an 0.3ml Microvette with clot activator, Sarsted, Germany) for insulin. After the fasting sample the subject will take 12 capsules or 2 tablets with a drink of 250ml water. Subjects will rest for 3-10min and have their blood pressure measured; 40min after swallowing the first capsule or tablet a finger-prick blood sample (2-3 drops for glucose and 6-8 drops for insulin analysis) will be collected and then subjects will consume 82.5g dextrose (containing 75g anhydrous glucose) dissolved in 300ml water within 5min plus a drink of 150ml water within 10min of starting the glucose drink. Further finger-prick blood samples for glucose (2-3 drops) and insulin (6-8 drops) will be obtained at 15, 30, 45, 60, 90 and 120 min after starting to drink the glucose solution. Venous blood samples (7ml) will be collected after the 60 and 120 min finger-prick. During the test subjects will remain seated quietly except for trips to the washroom if necessary. After the last blood sample subjects will be offered a snack and be free to leave.

Treatments

The 6 treatments administered will consist of the following:

- 12 placebo capsules with 250ml water (0g Axulin)
- 250ml water alone (0g Axulin)

- 4 placebo and 8 Axulin capsules (2g Axulin)
- 16 Axulin capsules (4g Axulin)

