- 2 Axulin tablets (2g Axulin)
- 4 Axulin tablets (4g Axulin)

Each placebo capsule contains 250mg inulin, each identical-looking Axulin capsule contains 250mg Axulin. It is anticipated that Axulin will be sold in tablets because 1g can be compacted into a tablet without loss of biological activity, but, because Axulin is a low-density powder, only 400mg can be placed in a capsule of similar size. We will use capsules in this study because it is more economical to produce the relatively small number of identical-looking placebo capsules required as compared to producing placebo tablets. To obtain doses in 1g increments, we will use smaller capsules containing 250mg each. The rationale for including tablets in the study is that Axulin in tablet form might be more slowly bioavailable than when encapsulated; thus, it is

important to determine whether the effects of Axulin tablets on postprandial responses is similar to the same dose taken in capsules.

Blinding

The number of Placebo and Active Axulin capsules and tablets required for the study will be provided to GI Labs. A person not involved in any other aspect of the study will make up 6 small zip-lock plastic bags for each subject labelled with a subject number and visit number and containing the treatment for visits 1 through 6 (the bag for the water alone treatment will be empty). The treatments will be randomized as shown in Table 1. The order of the blocks and the order of the treatments within each block were randomized using the @rand() function of Excel with 2 blocks of 6 created for lean subjects and 2 blocks for overweight subjects; the 2 extra orders are for use in case of drop-outs so that at least n=20 subjects complete the study (see Table 1). The person labeling and filling the bags with the treatments will assign the treatments to the codes and place the treatment assignments in a sealed opaque envelope kept in an accessible location. The envelope will be opened only after the study has been completed and the database locked, or in case of emergency if required for participant safety.

Table 1: Randomization Scheme

ID	Group	Visit 1	Visit 2	Visit 3	Visit 4	Visit 5	Visit 6
1	Lean	A	B	C	E	D	F
2	Lean	B	C	A	E	F	D
3	Lean	F	D	E	C	A	B
4	Lean	B	A	C	F	E	D
5	Lean	D	E	F	A	C	B
6	Lean	D	F	E	C	B	A
7	Lean	F	D	E	A	C	B
8	Lean	C	B	A	D	E	F
9	Lean	D	F	E	B	C	A
10	Lean	C	A	B	E	D	F
11	Lean	B	A	C	E	F	D
12	Lean	F	E	D	A	B	C
21	Overweight	D	E	F	C	B	A
22	Overweight	F	D	E	B	A	C
23	Overweight	A	B	C	E	D	F

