24	Overweight	A	C	B	F	E	D
25	Overweight	B	C	A	E	F	D
26	Overweight	C	A	B	D	F	E

27	Overweight	B	C	A	F	D	E
28	Overweight	D	F	E	B	A	C
29	Overweight	D	E	F	C	B	A
30	Overweight	F	E	D	A	B	C
31	Overweight	A	C	B	E	F	D
32	Overweight	E	D	F	C	A	B

Instructions: please assign capsules to codes A, B or C, and tablets or empty bag to codes D, E or F. Place treatment assignments into a sealed opaque envelope and keep the envelope in an accessible location. Treatments are as follows:

BLOCK 1 (A, B or C)

- Placebo 1; 16 Placebo capsules
- 2g Axulin caps: 4 Placebo capsules plus 8 Axulin capsules
- 4g Axulin caps: 16 Axulin capsules

BLOCK 2 (D, E or F)

- empty bag
- 2g Axulin tablets: 2 Axulin tablets
- 4g Axulin tablets: 4 Axulin tablets

Biochemical Analysis

Finger-prick blood samples for glucose analysis will be placed in the refrigerator immediately after being obtained and at the end of the test placed in a -20°C freezer until analysis which will be performed within 5 days. Glucose analysis is done using an YSI model 2300 STAT analyzer (Yellow Springs, OH). The microvette tubes used to collect blood for insulin analysis will be centrifuged at 3622×g for 2 min and the serum transferred to labeled polypropylene tubes and stored at -20°C prior to analysis of insulin using the Human Insulin EIA Kit (Alpco Diagnostics). Venous blood samples will be stored at 4°C until the end of the study after which they will be centrifuged at ~1400×g for 10 min and the plasma removed and separated into 2×1ml aliquots; 1 for analysis of triglycerides at St. Michael's Hospital biochemistry laboratory and the other for measurement of the active ingredient in Axulin by liquid chromatography/mass spectrometry.

Statistical Analysis

Incremental areas under the blood glucose, insulin and triglyceride response curves (AUC), ignoring area below fasting, will be calculated. Blood glucose and insulin concentrations and AUC values will be analyzed using repeated measures ANOVA examining for the main effects of dose, form (tablets vs capsules) and subject group (lean vs overweight) and their interactions. After demonstration of significant heterogeneity, differences between individual means will be assessed using Tukey's test to adjust for multiple comparisons.

Informed Consent

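### The planned ANOVA has no visit term, although the orders in Table 1 are unbalanced over visits in the tablet-and-water block; adding visit is a cheap improvement

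*Combined protocol and SAP*

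**What the plan says.** The Procedures section sets out a within-participant design: "Each subject will be studied on 6 separate days with at least a 3-day interval between tests". Three treatments form a capsule block and three form a tablet-and-water block. Under Blinding, "The order of the blocks and the order of the treatments within each block were randomized using the @rand() function of Excel". No balance of treatments over visits is stated.

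Table 1 prints 24 orders, 12 lean and 12 overweight. The person filling the bags is told: "please assign capsules to codes A, B or C, and tablets or empty bag to codes D, E or F". The treatment behind each letter stays in a sealed envelope until database lock. Of the 24 orders, "the 2 extra orders are for use in case of drop-outs so that at least n=20 subjects complete the study". The two spare orders are not identified.

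The Statistical Analysis section specifies a "repeated measures ANOVA examining for the main effects of dose, form (tablets vs capsules) and subject group (lean vs overweight) and their interactions", with Tukey's test to follow. It contains no visit, period or sequence term, and no rule for participants who complete only some visits.

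**The concern.** In a six-visit crossover, responses may differ by visit for reasons unrelated to treatment; unfamiliarity with the test on the first day is the obvious example. If each treatment falls equally often at each visit, such an effect cancels from the treatment contrasts. If not, and visit is not modelled, part of it is credited to treatment.

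The imbalance here lies mainly in D, E and F, the codes from which the tablet effect against water and the difference between tablet doses are estimated. Those codes also supply the tablet side of the capsule-versus-tablet comparison, which is one of the other objectives. Visit variation would also stay in the error term.

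**Working it through.** **The plan's own figure.** Number of subjects gives: "Using the t-distribution with 2-tailed $p<0.05$ and assuming an average CV of within-individual variation of 2-hour incremental AUC values of 25"%. Detectable difference = (t(0.975, 19) + t(0.80, 19)) × SD / √n = (2.093 + 0.861) × 25 / √20 = 16.5%, which the plan gives as 17%. The figure reproduces when 25% is used as the SD of the within-participant difference. It serves below only as a yardstick.

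**Codes by visit, all 24 orders of Table 1.**

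| Code | V1 | V2 | V3 | V4 | V5 | V6 |
|---|---|---|---|---|---|---|
| A | 4 | 4 | 4 | 4 | 4 | 4 |
| B | 5 | 3 | 4 | 3 | 5 | 4 |
| C | 3 | 5 | 4 | 5 | 3 | 4 |
| D | 6 | 4 | 2 | 2 | 4 | 6 |
| E | 1 | 5 | 6 | 7 | 3 | 2 |
| F | 5 | 3 | 4 | 3 | 5 | 4 |

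E is at visits 3-4 in 6 + 7 = 13 orders and D in 2 + 2 = 4. In the 12 lean orders E is never at visit 1 or visit 6. The single E at visit 1 is the row "32 Overweight E D F C A B".

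**Which orders are used.** The plan recruits 11 + 11 and needs 20 to complete. Three sets are therefore considered: all 24; 22 (orders 1-11 and 21-31); and 20 (orders 1-10 and 21-30). The last two assume that the spare or unused rows are the last in each group. Visit-1 counts are D 6, E 0, F 4 in both of these sets.

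**Shift from a first-visit effect.** The six dose-by-form cells are the six codes, and each participant receives each code once. For a first-visit effect δ, the shift in a contrast X-Y without a visit term is therefore δ × (count of X at visit 1 − count of Y at visit 1) / n. A least-squares fit with participant and treatment gives the same fractions.

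- D-E: (6−1)/24 = 0.208; (6−0)/22 = 0.273; (6−0)/20 = 0.300.
- E-F: (1−5)/24 = −0.167; (0−4)/22 = −0.182; (0−4)/20 = −0.200.
- D-F: (6−5)/24 = 0.042; (6−4)/22 = 0.091; (6−4)/20 = 0.100.
- Largest within the capsule block (B-C): (5−3)/24 = 0.083; (5−3)/22 = 0.091; (4−3)/20 = 0.050.

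The documents give no value for δ, so a range is assumed, in points where 100 is the mean AUC:

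| Assumed δ | D-E, 24 orders | D-E, 22 orders | D-E, 20 orders |
|---|---|---|---|
| 5 | 1.0 | 1.4 | 1.5 |
| 10 | 2.1 | 2.7 | 3.0 |
| 20 | 4.2 | 5.5 | 6.0 |

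**Steady drift.** With all 24 orders every code has the same mean visit number. For D it is (6×1 + 4×2 + 2×3 + 2×4 + 4×5 + 6×6)/24 = 3.5, and for E it is (1×1 + 5×2 + 6×3 + 7×4 + 3×5 + 2×6)/24 = 3.5. A linear trend therefore cancels. With 20 or 22 orders it leaves under 1 point per 10 points of total drift.

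**With visit in the model.** Visit is estimable in all three sets, and every shift above becomes zero. With a residual SD of 25, the standard error of D-E rises from 7.22 to 7.50 (24 orders, 4%), from 7.54 to 7.98 (22 orders, 6%) and from 7.91 to 8.31 (20 orders, 5%). For contrasts within the capsule block the rise is under 1%. In a separate fit to the 12 lean orders, the D-E rise is about 8%.

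**The case against.** The orders were randomised, so the contrasts are unbiased over the randomisation and this imbalance is chance. That is true, but the list has already been drawn and printed. Given this list, the share of a first-visit effect that enters each contrast is known, and adjusting for visit removes it.

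The likely size is modest. Conditions before each visit are standardised, no visit effect is documented, and even the 3.0-point shift is about 0.4 to 0.5 of a standard error at n=20 (3.0/7.91 = 0.38 with 25% as the residual SD; 3.0/5.59 = 0.54 with 25% as the SD of the difference, 25/√20 = 5.59). The double-blind capsule block and D-F barely move. All of this stands, and it limits the point to an improvement.

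A reader might infer three stronger claims that the documents do not support:

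- That E never occurs at visit 1. Order 32 has it there. It drops out only if order 32 goes unused, and the plan does not say which orders are the spares.
- That the tablet effect is biased in a known direction. The code is sealed, so D-E could be water against a tablet dose or one tablet dose against the other.
- That the analysis discards everyone without all six visits. A classical repeated measures ANOVA would do so, but the plan does not state it. What can be said is that the handling of partial data is unspecified, while withdrawal is allowed at any time and 10% dropout is expected.

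**Conclusion.** The point holds as a cheap improvement. The model omits visit, and the printed orders are clearly uneven over visits for D, E and F. Between 21% and 30% of any first-visit effect would enter D-E, and 17% to 20% would enter E-F. At an assumed 10 points that is 2.1 to 3.0 and 1.7 to 2.0 points, against a stated detectable difference of 17%. D-F moves by 0.4 to 1.0 points and contrasts within the capsule block by at most 0.9.

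These figures rest on two assumptions: the size of the first-visit effect, which the documents do not give, and which orders are used. They do not show that any result would be wrong.

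**What to change.** Add visit (1 to 6, categorical) as a fixed effect in the AUC model, beside dose, form, group and their interactions. Fit it as a linear mixed model with random effects for participant and participant-by-block, and state that all observed visits are included. The second part is secondary; it settles how partial data enter the analysis.

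The cost is one sentence, 5 degrees of freedom and the standard-error increases shown above: at most about 6% for D-E in the whole sample, and more if visit is estimated within the lean group alone.

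Optionally, if enrolment has not begun, redraw Table 1. In each group, use six capsule-first and six tablet-first orders, with each of the six within-block permutations used once in each block position. Each code then falls exactly twice at every visit. Exact balance holds only if all 12 orders per group are used. With 11 recruited and 10 expected to complete it will be approximate, so the visit term should stay in the model either way.

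### Tablet-versus-capsule similarity is addressed only by difference tests without confidence intervals, and on the implied coding one third of the form effect is water versus inulin capsules

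*Combined protocol and SAP*

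**What the plan says.** All references are to the combined protocol and SAP.

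- **The question.** Objectives lists, among its other objectives, whether capsules and tablets have similar effects on postprandial responses. Treatments gives the reason: tablets are the form expected to be sold and may be absorbed more slowly, so they should be compared with the same dose in capsules.
- **The layout.** Procedures describes a double-blind capsule block, and says that "the other block, which will be open label, will test the effect of Axulin tablets". Blinding notes that "the bag for the water alone treatment will be empty". The Table 1 instructions read "please assign capsules to codes A, B or C, and tablets or empty bag to codes D, E or F". Treatments labels both water alone and placebo capsules as 0 g Axulin. Each placebo capsule holds 250 mg inulin.
- **The analysis.** Statistical Analysis plans a repeated measures ANOVA for "main effects of dose, form (tablets vs capsules) and subject group (lean vs overweight) and their interactions". It continues: "After demonstration of significant heterogeneity, differences between individual means will be assessed using" Tukey's test. No confidence interval, similarity margin or separate form contrast is given.
- **The sample size.** Number of subjects claims "80% power to detect a 17% difference in AUC, 90% power to detect a difference of 19" per cent with 20 subjects. It makes no power claim for form.

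**The concern.** There are two linked difficulties.

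1. The question is one of similarity, but the form main effect, the dose-by-form interaction and the Tukey pairs all test for a difference. If they are not significant, the reader has no interval from which to judge how large a tablet-capsule difference remains possible.
2. The form main effect averages over three dose levels, and at 0 g there is no tablet. If the empty bag fills the 0 g tablet cell, that level compares plain water with inulin capsules. The average can then dilute a real tablet-capsule difference, or produce a form effect when tablets and capsules are identical.

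What is at stake is the conclusion about the form expected to be sold. The primary endpoint is not affected.

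**Working it through.** **Notation.** d2 and d4 are tablet minus capsule at 2 g and 4 g, and d is their common value. d0 is water minus placebo capsules. All are in percentage points of AUC. The documents give no value for any of them, so every effect below is an assumption.

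**Inputs.** From Number of subjects: n = 20, two-sided 5%, t-distribution, within-individual CV 25%.

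**Reproducing the plan's figures.** Let s be the SD of a paired difference. With s = 25, the difference detectable at 80% power is (2.093 + 0.861) × 25/√20 = 16.5. At 90% and 99% power, noncentral t gives 19.1 and 25.3. The plan states 17, 19 and 26. If 25% is instead the CV of a single test, s = 25 × √2 = 35.4 and the values are 23.4, 27.0 and 35.8, which do not match. The plan's figures therefore rest on s = 25. Both values are carried, because the wording also fits the second.

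**Standard errors** (complete data, equal variances, no subject-by-form variation):

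- Six-cell form effect, (d0 + d2 + d4)/3: s/√60 = 3.23 or 4.56.
- Four-cell contrast, (d2 + d4)/2: s/√40 = 3.95 or 5.59.

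**Chance of significance** (noncentral t, 19 df):

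| Assumed d, d0 | Six-cell signal, (2d + d0)/3 | Six-cell, s = 25 / 35.4 | Four-cell, s = 25 / 35.4 |
|---|---|---|---|
| 15, 0 | 10 | 84% / 55% | 95% / 72% |
| 0, 15 | 5 | 31% / 18% | 5% / 5% |
| 15, 15 | 15 | 99% / 88% | 95% / 72% |
| 15, −15 | 5 | 31% / 18% | 95% / 72% |

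Break-even: (2d + d0)/3 × √60 = d × √40, so d0/d = 3√(2/3) − 2 = 0.45. If d0 has the same sign as d and exceeds 0.45d, the six-cell test has more power.

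**Other planned routes, at d = 15 and d0 = 0.**

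- Dose-by-form interaction: noncentrality 20 × (10² + 5² + 5²)/s² = 4.8 or 2.4. With 2 and 38 df, power is 45.5% or 24.6%.
- Tukey (six means, 95 df, critical t 2.909): one named same-dose pair is significant 42% or 16% of the time, and at least one of the two pairs about 65% or 30% (simulation).
- Gating on the overall F test leaves single-pair Tukey power almost unchanged: 41.6% against 41.6%, or 16.2% against 16.0%.

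**What intervals would give.**

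- Pooled 95% half-width: 2.093 × 3.95 = 8.3, or 2.093 × 5.59 = 11.7.
- One dose: 2.093 × s/√20 = 11.7 or 16.5.
- Change-from-0 g contrast, (d2 + d4)/2 − d0: SE = s × √(1.5/20) = 6.85 or 9.68, half-width 14.3 or 20.3.
- With an assumed subject-by-form SD of 15 points, the pooled SE is √(s²/40 + 15²/20) = 5.18 or 6.52, and the half-width 10.9 or 13.6.

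**Block order.** In Table 1, 12 of 24 sequences begin with capsules (6 of 12 in each group), so block order is balanced against form.

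**The case against.** The case on the other side is substantial, and much of it stands.

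- **A reader might infer that the form factor is undefined.** The documents do not support that. Procedures, Treatments and the Table 1 instructions together imply a three-by-two layout with water as the 0 g tablet cell. One sentence would settle it.
- **A reader might infer that the Tukey gate blocks the same-dose comparison.** With an overall F test as the gate, it costs almost nothing. It could matter only if heterogeneity means the form or interaction term, which the plan does not specify.
- **A reader might infer that a false form effect is to be expected.** It needs a water-inulin difference, for which the documents give no value. With d0 = 0 there is no false signal.
- **The plan has another route.** If an effect means a change from 0 g, the dose-by-form interaction addresses the wording in Objectives. That is fair. However, its two 0 g references differ (inulin and water), so it estimates d − d0. With d = 0 and d0 = 15, the corresponding pooled contrast is significant 55% or 31% of the time.
- **Nothing says that non-significance will be read as similarity, and form is one of the other objectives with no power claim.** Both are true, and they limit the severity. They do not supply an interval for a question that the protocol itself calls important.

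**Conclusion.** The point holds as a minor, inexpensive improvement. The plan asks about similarity at the same dose and provides only difference tests without intervals. On the coding that its layout implies, one third of the form main effect has nothing to do with tablets or Axulin. Under the assumed 15-point difference with equal 0 g conditions, this lowers power from 95% to 84%, or from 72% to 55%. The size and direction of the distortion depend on d0, which is unknown, and for d0 above 0.45d the six-cell test would have the advantage in power. The primary endpoint and the sample size are not called into question. The figures assume 20 complete subjects, equal variances and no subject-by-form variation. With a subject-by-form SD of 15 points, 84% against 95% becomes 53% against 78%, and 55% against 72% becomes 39% against 59%.

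**What to change.** - State that the empty bag is the 0 g cell of the tablet block, if that is what is meant.
- Within the planned repeated-measures model, base the form comparison on tablet minus capsule at 2 g and 4 g, pooled and per dose. Give 95% confidence intervals taken from each contrast's own between-subject error, and report them whatever the omnibus result.
- Label the comparison descriptive, unless a similarity margin is justified before unblinding. If the forms are truly equal, the pooled interval would lie within an illustrative ±15 points 90% or 45% of the time (s = 25 or 35.4).
- Report water versus placebo capsules separately. Also report the change-from-0 g contrast with its interval, noting that its 0 g references differ.
- State two limits that no contrast removes. Form is confounded with open-label versus double-blind administration. The 2 g capsule treatment also contains 4 × 250 mg = 1 g inulin, so only the 4 g pair is free of inulin.

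**Cost.** Analysis wording and a few more estimates, with no new data. The form standard error rises from 3.2 to 4.0 points (or 4.6 to 5.6), and power is lost if d0 exceeds 0.45d in the same direction.

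As a separate point, the placebo treatment has 12 capsules in Treatments and 16 in the Table 1 instructions. The two passages must be reconciled.

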Pre-diabetes and Type II diabetes involve an impaired post-receptor response to insulin that hinders the glucose uptake response after meal consumption.¹⁷⁻¹⁹ Chronic hyperglycemia and the resulting compensatory hyperinsulinemia promote a cohort of acute and chronic sequelae including cardiovascular disease, liver complications, central nervous system degeneration and hyperglycemic osmotic stress.²⁰⁻²³ Axulin is a natural health product consisting of a mixture of extracts from herbs and vegetables present in normal diets which was identified by screening more than 100,000 compounds and extracts in a patented cell-culture based assay system targeting the IRS proteins. In vitro, Axulin has marked effects on the IRS-2 branch of the insulin signaling cascade to enhance downstream insulin signaling. Axulin has been shown in animal models to increase glucose uptake in peripheral tissues and decrease circulating blood glucose and triglyceride concentrations. Regular supplementation of the diet with Axulin would be expected to reduce the incidence of associated pre-diabetic and diabetic complications, resulting in an increased quality of life for patients without resorting to current anti-diabetic prescription drugs such as metformin and others that may have substantial unwanted side effects in patients.

HYPOTHESES

Axulin will reduce postprandial glucose and insulin responses in a dose-dependent fashion in healthy subjects without diabetes. The reduction in glucose and insulin will be relatively greater in insulin-resistant than insulin-sensitive subjects.

OBJECTIVES

The primary objective of this study is to determine the dose of Axulin which will reduce the incremental area under the blood glucose response curve (AUC) elicited by 75g oral glucose in healthy subjects by $\geq 33\%$.

The secondary objectives are to determine the dose-response effects of Axulin on:

- blood glucose and serum insulin AUC
- % reduction of insulin AUC
- the blood glucose and serum insulin increments at 15, 30, 45, 60, 90 and 120min
- insulinogen index
- Matsuda insulin sensitivity index
- ISSI-2 index of beta-cell function
- incremental blood lipid response at 120min
- plasma triglyceride response
- plasma axulin response

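### Dose-dependence is hypothesised and n=20 rests on single contrasts, but dose is tested only as an unordered factor: add a pre-specified linear dose contrast and keep Tukey

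*Combined protocol and SAP*

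**What the plan says.** Under HYPOTHESES the protocol predicts an ordered response: "Axulin will reduce postprandial glucose and insulin responses in a dose-dependent fashion in healthy subjects without diabetes". Under OBJECTIVES, "The secondary objectives are to determine the dose-response effects of Axulin on" a list headed by glucose and insulin AUC. The primary objective is a different question: "to determine the dose of Axulin which will reduce the incremental area under the blood glucose response curve" by at least 33%.

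The section Number of subjects justifies n=20 with t-based detectable differences at two-sided 0.05. It gives 17%, 19% and 26% for 80%, 90% and 99% power, 25% within a group of 10, and 33% between lean and overweight subjects.

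The Statistical Analysis section plans a repeated measures ANOVA, "examining for the main effects of dose, form (tablets vs capsules) and subject group (lean vs overweight) and their interactions". The follow-up is conditional: "After demonstration of significant heterogeneity, differences between individual means will be assessed using" Tukey's test. There are three dose levels (0, 2 and 4 g), each given in a capsule block and in a tablet block. No section specifies a trend test or an ordered contrast, or says what result would count as dose-dependent.

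**The concern.** The dose F-test has 2 degrees of freedom and ignores order: swapping the 2 g and 4 g labels leaves it unchanged. It is therefore equally significant for a rising pattern and for its reversal. Order enters the plan only through Tukey's pairs, whose critical value protects all pairwise comparisons of doses with no presumed order. The dose-by-group interaction likewise spends 2 degrees of freedom on a question that the hypothesis reduces to one contrast.

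At stake is a mismatch between the power that justified the sample size and the analysis that will be run. The stated power belongs to single contrasts at 0.05. The planned tests use the same data less efficiently for the hypothesis the sponsor wrote down, and the report has no rule for calling a response dose-dependent.

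**Working it through.** **1. Reproduce the plan's figures.** Inputs from Number of subjects: CV 25%, two-sided 0.05, n=20 (10 + 10). Detectable difference = (t₀.₉₇₅ + t_power) × SD/√n, with 25% used directly as the SD of the paired difference.
- n=20, 80%: (2.093 + 0.861) × 25/√20 = 2.954 × 5.590 = 16.5 (stated 17)
- n=20, 90%: (2.093 + 1.328) × 5.590 = 19.1 (stated 19)
- n=20, 99%: (2.093 + 2.539) × 5.590 = 25.9 (stated 26)
- n=10, 80%: (2.262 + 0.883) × 25/√10 = 24.9 (stated 25)
- Lean versus overweight: (2.101 + 0.862) × 25 × √(2/10) = 33.1 (stated 33)

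All five round to the stated values, so each is the power of one contrast with SD 25%.

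**2. Which SD applies to the planned dose effect?** The ANOVA dose effect averages over two forms, and the documents do not settle the SD of the averaged contrast.
- If 25% is the CV of a single AUC, the difference has SD 25 × √2 = 35.4% for one form, and 35.4/√2 = 25% averaged over two.
- If 25% is already the SD of one paired difference, it is 25% for one form and 25/√2 = 17.7% averaged over two.

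**3. 4 g versus 0 g, linear response (0, 8.5%, 17%), SD 25%.** Noncentrality = 17/(25/√20) = 17/5.590 = 3.04. Critical values are 2.10 (contrast, 18 df), 2.03 (contrast, pooled 36 df) and 2.44 (Tukey, three means, 36 df). For this shape the F-test has noncentrality 3.04² = 9.2, spread over 2 df.

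**4. Lean–overweight difference of 33 points at 4 g, linear in dose, SD 25%.** Noncentrality = 33/(25 × √(2/10)) = 33/11.18 = 2.95. The 2-df interaction has 2.95² = 8.7.

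Power from noncentral t and F; the gated Tukey figure is from 40,000 simulated trials:

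| Question | Test | SD 25% | SD 17.7% |
|---|---|---|---|
| 4 g vs 0 g, true 17% | single contrast | 82–84% | 98.2–98.7% |
| | F gate, then Tukey | 71% | 96.1% |
| Lean–overweight, true 33 points | single contrast | 80–82% | 97.6–98.2% |
| | 2-df interaction | 72% | 95.7% |

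The ranges reflect 18 or 36 error df. For one form alone with SD 35.4%, the 17% comparison is 55% by contrast and 38% by gate plus Tukey. At a true 33% with SD 25%, every test of 4 g versus 0 g is close to 100%.

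**5. Other shapes, SD 25%.**
- Plateau (0, 17, 17): F 86%, contrast 82–84%.
- Effect at 2 g only (0, 17, 0): F 86%, Tukey 2 g vs 0 g 72%, contrast about 5%, its nominal error rate.
- Reversed (0, 33, 16.5): F about 100%. The contrast has noncentrality 16.5/5.590 = 2.95 and is significant in 80–82%.

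With doses 0, 2 and 4 g the linear contrast has weights −1, 0, +1, so it is 4 g minus 0 g. The reversed case shows that it cannot by itself establish that 4 g beats 2 g; that still needs the 4 g versus 2 g pair.

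**The case against.** ANOVA with Tukey is a valid analysis, and dose-response effects can be described by estimating each dose. Two stronger readings are tempting, and the documents support neither.

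**That the plan would pass off a reversed pattern as dose-dependent.** The Statistical Analysis section never says that a significant F shows dose-dependence. It goes on to Tukey, which is directional. With true reductions of 33% at 2 g and 16.5% at 4 g (SD 25%), Tukey flags 4 g as worse than 2 g in 69% of trials and essentially never shows it as better. The plan lacks a rule for the ordered claim; it is not blind to order.

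**That Tukey should give way to a fixed sequence (4 g vs 0 g, 2 g vs 0 g, 4 g vs 2 g).** At SD 25% and true reductions of 16.5% and 33%, the sequence shows the full order in 61% of trials against 43% under the plan. That gap shrinks to 95% against 91% at SD 17.7%. With a 16.5% plateau there is no gain for 2 g versus 0 g (68% against 69%). If only 2 g works (16.5%), its detection falls from 69% to about 2.6%, because the sequence stops at 4 g. The primary objective is to find an effective dose, not a trend, so that is a poor exchange.

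The objection also stands on size: no dose-response shape is given, and the gain is small under the more favourable SD.

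**Conclusion.** The concern holds as a mismatch between hypothesis, power basis and test, and as an inexpensive improvement. It does not invalidate the analysis. Against one pre-specified contrast, the planned route loses about 11–13 points for a 17% effect at 4 g (71% against 82–84%) and about 8–10 points for a 33-point lean–overweight difference (72% against 80–82%). These losses assume a linear response, n=20 and a contrast SD of 25%. At SD 17.7% they are about 2–3 points.

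The gap concerns the dose-dependence hypothesis and the secondary dose-response objectives. The primary objective is not a trend question and is better served by the individual dose comparisons.

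**What to change.** In Statistical Analysis, for glucose AUC and insulin AUC:
- Add a pre-specified linear dose contrast (4 g minus 0 g) at two-sided 0.05 as the test of the dose-dependent hypothesis, not conditional on the omnibus F-test.
- Test the lean–overweight difference in effect by comparing that same contrast between the groups.
- Keep the ANOVA and Tukey for the individual dose comparisons, including 2 g versus 0 g for the primary objective.
- State that 4 g will be said to exceed 2 g only if that Tukey pair is significant in the predicted direction.
- Do not replace Tukey with a gated sequence.

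The cost is SAP wording; subjects, visits and data are unchanged. The contrast has little power for a non-monotone response and slightly less than the F-test for a plateau, and the retained ANOVA and Tukey cover those cases. Because 4 g versus 0 g is then tested both ways, the SAP should say that the contrast carries the hypothesis and that Tukey serves the dose-by-dose comparisons.
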